## HUMAN SUBJECTS

The study will enroll 200 participants, with the following inclusion criteria: a) at least 18 years of age; b) have access to a web-based device (e.g., computer; smartphone); c) be in-home caregivers of a loved-one with probable Alzheimer's Disease (AD) or related dementia, d) be living with their care recipients; and e) providing a minimum of 20 hours of care per week. Participants will be excluded if: a) the caregiver or ADRD patient is diagnosed with a terminal illness with a life expectancy of less than 1 year, b) caregivers are cognitively impaired as measured by a brief screen for cognitive functioning; i.e., a Mini Mental State Exam (MMSE) score of  $<27$ , c) caregivers are enrolled in another intervention study or are already receiving psychotherapy to improve well-being or reduce distress. The sample will be recruited from: a) the UCSD Alzheimer's Disease Research Center, b) community-based organizations with whom our research team already has well-established relationships (e.g., the San Diego chapter of the Alzheimer's Association; the Southern Caregiver Resource Center); and c) community support groups. Participants will be of varied gender and ethnicity.

## RECRUITMENT AND PROCEDURES PREPARATORY TO RESEARCH

The primary referral source is the UCSD Alzheimer's Disease Research Center (ADRC). Added recruitments occur following informational meetings with various community based organizations serving the Alzheimer community and the elderly. At the ADRC caregivers will either be assessed by ADRC staff to determine if they are appropriate for inclusion in this study when they are enrolled into the ADRC, or by our staff. The ADRC has evaluated over 2,000 Alzheimer Disease patients to date, and these individuals are often brought by their caregivers to appointments. Thus, in this situation, ADRC staff will explain our study to the caregiver and, if the caregiver is appropriate for inclusion into the study, a staff member will describe the study to the potential participant.

Subjects will also learn of the study via IRB-approved online advertisements, through our lab web site, or through web sites such as Research Match or ClinicalTrials.gov. In these cases, subjects will call our lab phone number and will be screened over the phone and, should they meet inclusion criteria and express interest in joining the study, they will be sent the consent form via mail, e-mail, or fax. A member of our research lab

witllwill go over the consent form verbally with the participant, and participants will then complete the consent form and return either by US Mail, e-mail (by scanning a copy of their consent and e-mailing), or by fax.

In all cases, fully informed consent will be obtained, and [name] and other co-investigators will be directly available to clarify questions should any be raised by the participant. Signed consent forms will be kept on file in a specially secured cabinet. All of the investigators have completed the required federal human subjects certification.

## **INFORMED CONSENT**

If a subject is appropriate for inclusion into the study, a staff member describes the study, including questionnaires, assessments, and the glucose measurement. The consent will detail the purpose of the project and its minimal risks. Also, participants will be informed that participation in the project is voluntary and they will be afforded the opportunity to discontinue their participation without consequences at any time during the project. Signed consent forms will be printed and kept on file in a specially secured cabinet. Participants who call in to our lab from online recruitment advertisements, from our lab web site, Research Match, or Clinicaltrials.gov will be screened over the phone for eligibility, and a copy of our consent form will be mailed, e-mailed, or faxed to them. A member of our research team will go over the consent verbally by phone, and a signed copy of the consent will be mailed, e-mailed, or faxed back to our lab. Those participants who wish to discontinue the project will be provided referrals to other agencies that can provide them with services.

## **ALTERNATIVES TO STUDY PARTICIPATION**

The alternative to participation is not to participate.

## **POTENTIAL RISKS**

We anticipate the risks associated with this study will be minimal. However, participation in this study may involve some added risks or discomforts. These include the following:

- 1) *Boredom and fatigue* – Participation in the online assessments may require time and attention, and participants may become bored or fatigued. If this happens, participants will have the right to take a break to rest. They may also discontinue the interview and resume at a later date..
- 2) *Distress* – During the assessments, we will be asking questions about stress and mood experiences. Discussion of these experiences may be distressing. If this occurs, they have the right to take a break and rest, to not to answer questions that produce distress, or to discontinue the assessment. Again, staff will proactively inquire to participants every 20-30 minutes if they would like to take a break, discontinue, or postpone the assessment. Staff will also be trained by the PI to recognize non-verbal cues of discomfort and will be informed to discontinue assessments where clear distress is displayed by participants.
- 3) *Loss of Confidentiality* - There is a small potential for the loss of confidentiality but the following steps will be taken to minimize it: Assessment interviews will be conducted online and participants will receive a user-specific code allowing them to complete their personal set of questionnaires. Questionnaires completed online will be encrypted for added security and stored data will be behind a data firewall for added security. Access to data will be through password that only study personnel will have. Privacy of data will be maintained by using a code identifier rather than participant name on any/all data and the codes will be unlinked with personal information. Only authorized personnel from the laboratory will have access to the data.. For the purposes of reports and publications, participant data and results will be presented only in pooled form, with no personal identifiers. However, there are some circumstances under which information may not be kept confidential. Specifically, if

our team believes there is reasonable risk that participants will harm themselves (e.g., commit suicide) or others, or if our team believes there is reason to believe abuse or neglect is being conducted toward anyone being reported on in this study (e.g., either the caregiver or the care recipient), we are required by law to inform authorities so that steps can be taken to reduce this risk. Therefore, confidentiality cannot be maintained in these circumstances.

4) *Unknown Risks* - Because this is a research study, there may be some unknown risks that are currently unforeseeable.

### **RISK MANAGEMENT PROCEDURES AND ADEQUACY OF RESOURCES**

1) *Boredom and fatigue* – Participation in the interviews may require time and attention, and participants may become bored or fatigued. If this happens, participants may take a break in order to rest. They may also ask to discontinue the assessment and resume at a later date.

2) *Distress* – During the assessments, we will be asking questions about caregivers experiences, including some of the stresses they have faced while providing care to their loved ones. Answering these questions may be distressing. If this occurs, they have the right to take a break and rest, to skip questions that produce distress, or to discontinue the assessment.

3) *Suicidal Ideation* - We have a standardized protocol for assessing and managing risk for suicidality. Our brief description of this protocol is as follows: During participant screening, participants will be assessed for suicidal ideation. Participants will be asked if they have recently (within the past month) had thoughts of (or considered) harming themselves or others. ‘Yes’ responses will be followed with clinical assessment of the nature of these thoughts, including whether the potential participant has the means of completing a suicide (e.g., access to a gun) or hurting others, and a plan (e.g., knows when and where he/she will act). Participants endorsing harm to self or to others will be managed clinically and will be referred to an appropriate mental health provider for further care. Participants endorsing clinically significant symptoms of depression ( $\geq 8$  on the HADS) will be monitored throughout therapy via regular check-ins by phone to evaluate the potential for suicidal ideation or self-harm. Participants with active suicidal thoughts or intent will be managed clinically, referred for appropriate psychiatric care, and discontinued from participation in this study.

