## **Measures**

***Blood Pressure:*** Blood pressure will be collected using an Omron HEM 907XL IntelliSense Professional Digital Blood Pressure Monitor sent to participants using US Mail or similar format. Blood pressure will be self-assessed by participants at baseline, 3-, 9-, and 15-months.

The following section details the information to be collected from caregivers via online administration. Further, we detail the specific time-points at which the information will be collected:

***Depressive Symptoms (Primary Outcome):*** Symptoms of depression will be assessed using the Center for Epidemiological Studies Depression Scale—Revised (CESD-R). The CESD-R is a 20-item scale that asks patients to rate the degree to which they have experienced several symptoms of depression over the past week. Scores of  $\geq 16$  correlate highly with a diagnosis of depression. The scale was revised to better reflect the diagnostic criteria of the DSM-5, and the scale continues to good psychometric properties. This scale addresses RFA-AG-18-030, as depressive symptoms is a key well-being outcome in caregivers. This scale will be administered at baseline, 3-, 9-, and 15-months.

***Positive and Negative Affect.*** We will utilize the Positive and Negative Affect Schedule (PANAS) to assess positive (PA) and negative affect (NA). The PANAS contains 20 items assessing PA and NA. Alpha reliability is excellent, ranging from .83-.90 for the PA scale and .85-.90 for NA. This scale addresses RFA-AG-18-030, which lists positive and negative affect as key outcomes to be assessed. This scale will be administered at baseline, 3-, 9-, and 15-months.

***Mental and Physical Well-Being:*** Mental and physical well-being will be assessed using the SF-12 scale, which is a multi-purpose, short form health survey consisting of 12 questions. Test-retest and internal reliability exceed 0.70 in studies of this scale's psychometric properties. The SF-36 also has excellent content, criterion, and predictive validity. This scale will be administered at baseline, 3-, 9-, and 15-months.

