A key element to keep participants engaged in the program is the use of text reminders. Each night, at a time of the participant’s choosing, a text is sent to participants with a hyperlink to their individualized web-portals. Along with the hyperlink is a message asking users to provide an update on their progress toward their goals for the week. In addition, for the first three months of using the mPEP intervention, participants will receive bi-monthly 10-minute “check-in” calls from a coach to answer questions on how to use the web site, problem-solve any barriers to participating in activities, and encourage participants to do their best to achieve their weekly goals. So as not to overburden caregivers, these check-in calls will be scheduled between the coach and caregiver at a time of the caregiver’s choosing. Participants complete a total of three phases in the project, which are (sample screen shots presented in Figure 3):

**Phase 1:** This phase involves self-monitoring activities over the course of one week. This phase is designed to capture activities the participants already engages in (and when), to help increase awareness of how balanced their lives are with regard to self-care activities vs caregiving activities. At the end of each day, participants complete an activity detailing when they woke up, activities they completed throughout the course of the day, and ratings of how enjoyable/pleasant each activity was. Each activity is entered into a personalized calendar so

they can visually see how they spent their day, as well as how many hearts they received from each activity.

**Phases 2 and 3:** These phases involve the selection and engagement in activities designed to promote overall well-being for the caregiver. In Phase 2, the participant completes a mood questionnaire of their positive and negative affect over the previous week. This is designed to provide participants with a baseline assessment of their well-being, on which to track progress as they move through the stages of the application. Following completion of the questionnaire, the participant receives feedback on all activities during phase 1 that were rated

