**Figure 3.**  
**Screenshots from mPEP.**  
Left = Phase 1 (self-monitoring), Middle = Phase 2 (activity selection); Right = Phase 3, activity tracking.

PEP

You woke up at 6:15 AM. What was your next activity?

[figure not shown]
[figure not shown]
Activity: Eat breakfast

Enter the activity duration or end time

Time  Duration

End time: 7:00 AM

hearts NEXT DAY DONE

*b. Information and Support Intervention* - Participants randomized to this condition will have personalized web access to a comprehensive resource guide containing materials on coping with specific CG stresses (e.g., developing problem-solving skills; managing care receiver problem behaviors; improving communication), and services available for caregivers in San Diego County (i.e., adult day care services; legal services for seniors; respite services). In this intervention, caregivers choose information most relevant to their current circumstances, accessible any time convenient to them. To ensure equivalent contact and support, for the first three months of using this intervention, participants will receive “check-in” calls every two weeks to answer questions on how to use the web site, problem-solve any barriers to participating in activities, and provide information and any referral to services. In addition, participants will receive a unique log-in key associated with their participant identification number, which will allow us to evaluate treatment compliance data and exposure to the treatment information (e.g., information accessed; time spent logged-in). Further, to ensure similarities in treatment delivery, participants will receive nightly text reminders to access and apply information learned at the web-site.

**Screening Procedures:** Screening will occur in person and will consist of a formal screening questionnaire assessing participant eligibility. In addition to the screening questionnaire, participants will be administered the mini-mental state exam (MMSE) to determine cognitive function and eligibility as per our eligibility criteria.

Participants scoring <27 on the MMSE will be informed they are not eligible to participate in the project.

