**PROCEDURES FOR SURROGATE CONSENT AND/OR DECISIONAL CAPACITY ASSESSMENT**

To assess decisional capacity of each participant, we will administer the UCSD Brief Assessment of Capacity to Consent (UBACC). After participants go over the informed consent in detail, they will complete an online set of 7 items assessing his/her understanding and appreciation of the information concerning a research protocol. For each answer provided by the participant, the research assistant scores participants on a scale of 0 (clearly incapable) to 2 (clearly capable response). For the current study, only participants scoring '2' for each of the 7 items will be enrolled in the study. Participants who do not score a '2' on the first try will be provided a second opportunity to score a '2'. Total time to administer this assessment is approximately 5 minutes.

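### Phone monitoring for suicidal ideation during therapy is triggered by a HADS score, but the plan never schedules the HADS

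*Combined protocol and SAP*

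**What the plan says.** Risk Management Procedures, item 3, sets out two safeguards that work differently.

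- The first applies at entry: "During participant screening, participants will be assessed for suicidal ideation". A positive answer leads to clinical assessment and, where needed, management and referral. No score is required.
- The second applies after entry. Caregivers with depression at a clinically important level, given as a score of 8 or more "on the HADS) will be monitored throughout therapy via regular check-ins by phone to evaluate the potential for suicidal ideation or self-harm". The only cut-off stated is a HADS score.

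The depression scale the trial schedules is a different one. Measures names the CESD-R as the primary outcome, cites a cut-off of 16 or more, and fixes its timing: "depressive symptoms is a key well-being outcome in caregivers. This scale will be administered at baseline, 3-, 9-, and 15-months".

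Screening Procedures says that screening "will consist of a formal screening questionnaire assessing participant eligibility", and adds the MMSE. The section on decisional capacity adds one more instrument: "To assess decisional capacity of each participant, we will administer the UCSD Brief Assessment of Capacity to Consent".

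**The concern.** The promised calls depend on a score that no listed procedure produces. Staff who follow the document would reach the start of therapy with no HADS result for anyone, and so with no stated basis for deciding who should be called.

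What is at stake is participant safety after entry. The trial enrols caregivers because of the distress that caregiving brings, and its primary outcome is depressive symptoms. The ideation question is asked at screening and no repeat is scheduled. The HADS-triggered calls are the only later contact whose stated purpose is to look for suicidal ideation or self-harm. If they never start, that scheduled check is lost for the caregivers it was written for.

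**Working it through.** There is no power or sample size figure to reproduce. The check is an inventory of instruments, followed by a search for anything that could take the place of the missing score.

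**1. Is the HADS scheduled anywhere?**

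| Place in the protocol | Named there | Count | HADS |
|---|---|---|---|
| Measures | Blood pressure, CESD-R, PANAS, SF-12 (an SF-36 mention is counted with it), ZBI short form, Role Overload, CDR, ADLQ, RMBPC | 9 | No |
| Screening Procedures | MMSE, plus an eligibility questionnaire with no item list | 1 | No |
| Decisional capacity | UBACC | 1 | No |

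The total is 9 + 1 + 1 = 11 named instruments, of which the HADS is 0. It is listed at 0 of the 4 survey points. Its single mention is the monitoring rule itself, which gives no time of administration.

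**2. Does another listed score feed the rule?**

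- *CESD-R.* It is collected before the intervention, but its cited cut-off is 16, not 8. Nothing in the protocol ties a CESD-R result to the monitoring calls.
- *App mood questionnaire.* Under Interventions, in Phase 2 of mPEP, "the participant completes a mood questionnaire of their positive and negative affect over the previous week". This measures affect, carries no cut-off for risk, and exists in the mPEP arm only.

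**3. Does another scheduled contact do the same job?**

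- *mPEP coach calls.* They answer website questions, "problem-solve any barriers to participating in activities, and encourage participants to do their best".
- *Control-arm calls.* They answer website questions, "problem-solve any barriers to participating in activities, and provide information and any referral to services".
- Neither set of calls is described as a suicide-risk check. Both run for the first three months, whereas the Assessments paragraph places post-therapy at 6 months, so they would not cover the whole of therapy even if given that purpose.
- *Breaks and distress checks during assessments* (Potential Risks, item 2). These address comfort during an assessment and schedule no question about suicidality.
- *Duty to inform authorities* (Potential Risks) and *the rule for active suicidal thoughts or intent* (Risk Management Procedures, item 3). Both work without the HADS, but only once staff know of the risk.

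**4. Would a high depression score reach staff anyway?**

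Surveys are completed online under a code, without identifying details. A key linking code to person exists (Privacy and Confidentiality Considerations), but no step says that anyone reads the baseline score promptly or uses the key to act on it.

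The rule therefore has no documented input, and no other scheduled step replaces it.

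**The case against.** The strongest reply is that the documents seen here are not the whole of the study's procedures. Item 3 presents itself as a short summary of a standing suicidality protocol, and the items of the screening questionnaire are not published. Screening Procedures also omits the ideation question, which item 3 places at screening, so it is plainly not a complete list. The HADS could be in either unseen form. This stands as a limit on what can be said about practice. It does not supply a documented trigger, and the remedy in that case is still a correction to the text.

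A second reply is that the intended group is clear, because the criterion is first stated in words, and that a usable depression score exists in the baseline CESD-R. The HADS may simply be wording carried over from another study. That is plausible, and it is why the fix is easy. But the only cut-off given belongs to the HADS, and the plan states no meaning for a score of 8 on the CESD-R.

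A third reply is that every caregiver in both arms is phoned every two weeks for the first three months, and that staff must act on any risk they come to believe in. This narrows the practical gap. It does not close it, because those calls have other purposes and end after three months.

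**Conclusion.** The concern holds. As documented, the only suicidality check scheduled after screening is triggered by a score that is never collected: 0 of 11 named instruments and 0 of 4 survey points. This is a rule that fails as written, and it should be fixed.

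The scope is limited. Protection at entry is intact, as are clinical management and referral, the rule for active suicidal thoughts or intent, and the duty to report. The gap is in score-triggered monitoring after entry. The number of caregivers affected would be 200 times the share above the cut-off, and the documents give no expected share, so no figure can be stated.

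The conclusion rests on the published text. If an unseen screening form does include the HADS, the defect is reduced to an undocumented source and time for the score.

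**What to change.** **Main change.** In Risk Management Procedures, item 3, replace the HADS trigger with a baseline CESD-R cut-off set by the clinical team. The 16 cited under Measures is one candidate. In the same place, name the existing study role that checks the baseline score promptly, re-links a flagged score through the key described under Privacy and Confidentiality Considerations, and starts the calls already promised. Potential Risks, item 3, says the codes will be unlinked from personal information; reword it to allow this use of the key.

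**Alternative.** If the HADS is already given at screening, add it to Screening Procedures with its timing. This costs one line.

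**Cost of the main change.** It needs wording in two sections, a check on data already being collected, controlled use of the linking key, and the calls the protocol already promises. It needs no new instrument or visit. A lower cut-off flags more caregivers and so means more calls. The baseline score precedes the intervention, so the trigger cannot depend on response to treatment.

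**Optional.** The same rule could be applied again at later surveys during therapy. The plan does not promise this, and it has a price: staff contact would then depend on the outcome, could affect later CESD-R scores, and could differ between arms.
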